4.2.2.5 Treatment Policy Strategy

Another supportive analysis will be performed on the primary efficacy endpoint to address IE.

The treatment policy strategy will include all available data observed at the week of interest (Week 16) regardless of the occurrence of IE. This means the analysis includes on- and off-treatment values collected after subjects prematurely discontinued study treatment but agreed to remain on the study and continued to attend visits and provide assessments at those visits. Those observed values will be analyzed according to the subject's randomized treatment. Subjects for whom efficacy data cannot be obtained at the week of interest, despite attempts to retain them in the study, will have their data imputed using MI-MCMC / monotone regression ([Section 4.2.2.2](#)) based on non missing data collected up to Week 16.

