4.2.2.2 MI – MCMC/Monotone Regression

In instances where MI is used, the missing value is replaced by a set of plausible values, where each value is a Bayesian draw from the conditional distribution of the missing data given the observed data. Intermittent missing data will be imputed using the MCMC method, followed by regression for monotone missing data (called “MI-MCMC/Monotone regression” method in this SAP). The MI procedures planned for efficacy analyses are based on an assumption of data missing at random (MAR).

This section describes the algorithms to be implemented for the MI – MCMC/Monotone Regression procedures for non-composite binary endpoints, composite binary endpoints, and continuous endpoints. These descriptions focus on the MI procedure itself and do not specifically account for dealing with IE ([Section 4.2.1](#)).

Non-composite binary endpoints

For non-composite binary endpoints, the MI method will be applied as follows:

- Step 1 - Imputation of missing data using MI

Create datasets, one for each treatment group, of subjects with observed values and missing values (needing estimation by MI). For the imputation step, missing values will be separated into 2 categories: intermittent missing values (ie, missing values for a given subject that has available data before and after the missing timepoint, including missing value at Baseline) and monotone missing values (ie, where all subject data is missing after a given time point). Datasets should be designed in a horizontal structure meaning that each subject should be presented in a single observation, with a set of values, one for each scheduled visit where the endpoint is scheduled to be collected according to the protocol (this exclude the unscheduled visits). For the Week 24 analysis, this will include visits up to Visit 14 (Week 24) and for the Week 52 analysis, visits up to Visit 28 (Week 52). Datasets should also be sorted by subject number before proceeding with the MI process.

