For the intermittent missing values, the missing value in each dataset will be filled in using the MCMC method with multiple chains, monotone missing data imputing pattern, and non-informative priors for all parameters. Unless specified differently, the first 200 iterations will not be used (the ‘burn-in’ option). A total of 100 sets of imputations will be performed. The seed used for these imputations will be 2017 and all other MI procedures described in this SAP will use this same seed as well. The procedure will be performed for each treatment group separately. The resulting 100 imputed datasets will have a monotone missing pattern and will be imputed using a method for monotone missingness.

For monotone missing data, one monotone regression will be used to impute missing data. A separate regression model is estimated for each variable with missing values (ie, measurement at each time point). Based on the resulting model, a new regression model is then drawn and is used to impute the missing values for the variable. Since the dataset has a monotone missing data pattern, the process is repeated sequentially for variables with missing values. The procedure will be based on the 100 imputed datasets generated from the MCMC procedure and will be performed for each treatment group separately by imputation. The SAS® PROC MI procedure will be used for the imputation.

In both cases, the imputation model will include the randomization strata as stratification variables (region and bone erosion at Baseline), the value at Baseline and at each post-Baseline visit (up to the week of interest). The imputation model based on the MCMC method will only allow joint multivariate normal variables. For the MCMC method (when imputing intermittent missing values), randomization strata will be re-coded as indicator variables and will always be specified in the following order: North America region (1 for North America, 0 otherwise), Western Europe region (1 for Western Europe, 0 otherwise), Eastern Europe region (1 for Eastern Europe, 0 otherwise). For each imputation model, Bone erosion at Baseline (0 if bone erosion at Baseline = 0 ; 1 if bone erosion at Baseline \geq 1).

Bone erosions will be read for all visits at both at the Week 24 analysis and the Week 52 / final analyses to ensure that unnecessary bias is not introduced. Given there may be differences at Baseline for a subject between the two sets of reads, the following rules will be applied for the MI process:

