4.2.2.3 MI – MCMC/Reference-based imputation

For the primary analysis of the secondary continuous efficacy variables included in the testing hierarchy and the individual components of the ACR response, the referenced-based multiple imputation method will be used. In this imputation method, the missing data will be imputed based on data from the placebo group only (Mallinckrodt, 2013). This analysis will be performed only for the subjects randomized to Placebo and BKZ.

Reference-based MI assumes that the statistical behavior of the BKZ and placebo randomized subjects after discontinuing study medication becomes that of the placebo-treated subjects. All time points after study treatment discontinuation for BKZ and placebo groups will be considered missing. MIs are used to replace missing outcomes for BKZ and placebo-treated subjects who discontinued using multiple draws from the posterior predictive distribution estimated from the placebo arm.

Note : SAS 9.4 may be used for this analysis where equivalent steps to those outlined below will be used to perform the imputation.

In the case of continuous endpoints, the procedure will be implemented as follows on the raw values:

1. Data will be processed sequentially, one timepoint (visit) at a time, by repeatedly calling SAS® PROC MI to impute missing outcome data at visits t=1 (Baseline), ..., Week 16 (Week 16 being the time point of interest) using data from the placebo-treated subjects only.
 - a. Initialization. Set t=1 (Baseline visit). Create a dataset combining all records from BKZ and placebo subjects with columns for covariates (bone erosion and region) and outcome at Baseline. Impute missing values at Baseline using bone erosion at Baseline, and region. Note that both placebo and BKZ data will be used to estimate the imputation model.
 - b. *Iteration.* Set t=t+1. Create a dataset combining records from BKZ subjects with missing data at visit t and all placebo subjects with columns for covariates (bone erosion and region) and

outcomes at visits 1 to t. In this dataset, outcomes for all BKZ randomized subjects are missing at visit t and observed or previously imputed values at visits 1 to t-1. Outcomes for placebo-treated subjects are observed or missing at visit t or observed or previously imputed values at visits 1 to t-1. The outcomes should be sorted in chronological order in the model.

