8.1.4.5 Analyses using treatment policy strategy imputation for missing data

The treatment policy strategy for addressing IE will be considered. This will be based on an analysis in which all available data at Week 16 regardless of the occurrence of IE will be kept in the analysis. This analysis will use the same models specified for the primary analyses where subjects are analyzed according to their randomized treatment, even if they discontinued study treatment for any reason prior to Week 16 and were no longer on the randomized study treatment when the assessment was performed at Week 16.

In the context of this analysis, in addition to the statistics provided in the context of MI, the number of observed ACR50 responses regardless of the occurrence of IE will be also reported.

The estimand for the treatment policy strategy analysis is detailed below:

- Population = Subjects enrolled according to the protocol-specified inclusion/exclusion criteria and randomized to IMP.
- Subject-level outcome = ACR50 at Week 16.
- IE handling = Discontinuation of study medication for any reason will be handled by using the data as observed irrespective of the IE occurring.
- Population-level summary measure = Conditional OR comparing ‘BKZ and other medication as needed’ to ‘placebo and other medication as needed’.

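### The treatment-policy analysis of ACR50 imputes Week 16 values missing after treatment discontinuation with an arm-wise MAR model that ignores discontinuation, so for those subjects it leans towards on-treatment response

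*SAP*

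**What the plan says.** SAP 8.1.4.5 defines the target: "Discontinuation of study medication for any reason will be handled by using the data as observed irrespective of the IE occurring". SAP 4.2.2.5 accordingly keeps on- and off-treatment Week 16 values and analyses them by randomized arm. Subjects with no Week 16 data "will have their data imputed using MI-MCMC / monotone regression", "based on non missing data collected up to Week 16". No distinction is made between a value missing while on drug and one missing after stopping, and 8.1.4.5 adds no other rule.

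The method referred to is in SAP 4.2.2.2. It assumes missing at random, and "The procedure will be performed for each treatment group separately". Its terms are region, bone erosion, the Baseline value and the earlier visit values. There is no discontinuation indicator, no restriction to subjects observed off treatment, and no reference-based step.

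SAP 8.1.4.4 applies two hypothetical strategies to the ACR components. Strategy (a) treats subjects as if they had completed treatment and uses this same imputation. Strategy (b) treats them as if they had completed on placebo and uses reference-based imputation. For the latter, SAP 4.2.2.3 says that "the missing data will be imputed based on data from the placebo group only".

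**The concern.** A treatment-policy estimate needs the outcome that discontinuers actually had. When that outcome is missing, the imputation should represent a subject who is off the drug. Here the Week 16 regression is fitted to the whole arm. If most BKZ subjects reach Week 16 on treatment, that regression describes on-treatment response, and a BKZ discontinuer's missing value is drawn from it.

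SAP 3.7 makes this the only analysis in which data collected after discontinuation are tabulated rather than just listed. It is the reader's one direct look at ACR50 regardless of discontinuation, and its imputed part leans towards BKZ. Agreement between this analysis and the primary one is weaker support than it appears.

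**Working it through.** **Inputs.** BKZ ACR50 rate 43.8%, placebo 16%, 420 and 280 subjects, stated power >99%, difference 27.8 points, OR 4.09 (all SAP 2.4.1). The SAP gives no discontinuation or missingness rate, so m, the share of the BKZ arm that stopped drug and has no Week 16 data, is assumed.

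**The plan's own figure.** OR = (0.438/0.562)/(0.16/0.84) = 4.09. Power for 420 vs 280, 2-sided 0.05, is above 99.9% with or without continuity correction. Both agree with the SAP.

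**Upper bound.** Suppose affected BKZ subjects are imputed at the on-treatment rate while their true off-drug rate equals the placebo rate. Then overstatement = m × (0.438 − 0.16) = 0.278 × m. The BKZ rate with off-drug imputation is (1 − m) × 0.438 + m × 0.16, and the placebo rate is held at 16%.

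| m (assumed) | BKZ rate, arm-wise MI | BKZ rate, off-drug at 16% | Overstatement (points) | OR, arm-wise vs off-drug |
|---|---|---|---|---|
| 2% | 43.8% | 43.2% | 0.6 | 4.09 vs 4.00 |
| 3% | 43.8% | 43.0% | 0.8 | 4.09 vs 3.96 |
| 5% | 43.8% | 42.4% | 1.4 | 4.09 vs 3.87 |
| 8% | 43.8% | 41.6% | 2.2 | 4.09 vs 3.74 |
| 15% | 43.8% | 39.6% | 4.2 | 4.09 vs 3.45 |

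**Does arm-wise imputation behave this way?** It was simulated as a sequential regression in one arm of 420: visit correlation 0.6, stopping after Week 8, off-drug response back to the placebo rate by Week 16, 5% to 15% stopping, and 0%, 30% or 50% of stoppers retained with off-drug data. Stoppers without Week 16 data were imputed as responders 41.5% to 44.5% of the time, against a true off-drug rate of 15.4% to 16.5%. Retained off-drug data lowered the imputed rate only slightly, because the model does not separate on- from off-drug subjects. The simulation makes stopping unrelated to earlier response and assumes full loss of effect by Week 16, so it confirms the direction and the upper bound, not the likely size.

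**Does Step 3 of 4.2.2.2 repair it?** That step sets visits after an intercurrent event to non-response, whether observed or not. Applied here, it would overwrite the off-treatment data that 4.2.2.5 keeps. SAP 4.2.2.2 also says its descriptions do not specifically deal with intercurrent events. It is not a remedy, and 4.2.2.5 should say so.

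**The case against.** A reader might infer that the plan contradicts SAP 4.2.2.3, where "Reference-based MI assumes that the statistical behavior of the BKZ and placebo randomized subjects after discontinuing study medication becomes that of the placebo-treated subjects". It does not. That assumption belongs to reference-based imputation of the continuous hierarchy endpoints and the ACR components. SAP 4.2.1.3 plans supportive analyses under different missing-data mechanisms on purpose, and 8.1.4.4 runs both assumptions on the same components.

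Nor is the whole analysis simply the hypothetical strategy. Under that strategy observed post-discontinuation data are set to missing. Here they are kept, and they enter the imputation model. Only discontinuers without Week 16 data are affected.

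The 27.8-point gap is not the expected bias either. Imputation conditions on the subject's earlier visits, so a poor course before dropout lowers the imputed response. SAP 10.1.1.2 gives 140 days as 5 half-lives, so one half-life is 28 days: a subject last given active drug at Week 8 is 56 days, or two half-lives, away at Week 16. The estimand also allows other medication as needed, so the true off-drug rate may exceed 16%.

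The optimism is bounded elsewhere too. The primary analysis counts every missing or post-discontinuation BKZ value as non-response, which is harsher than 16%. The first step of the tipping-point analysis (4.2.2.4) additionally sets placebo subjects with missing ACR50 to response.

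All of this stands and limits the consequence. What remains is that, for discontinuers without Week 16 data, the method is the one the SAP uses elsewhere for subjects assumed to have completed treatment.

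**Conclusion.** The point holds as a mismatch between target and method in one supportive analysis. For discontinuers without Week 16 data, the imputation leans towards on-treatment response. The BKZ ACR50 rate is overstated by at most 0.278 × m, which is 0.8 to 2.2 points for an assumed m of 3% to 8%. This rests on the planning rates, on off-drug response equal to placebo, and on no help from earlier visits; the real figure should be smaller. That the arm is mostly on drug at Week 16 is an inference, since the SAP states no discontinuation rate.

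A reader might go on to doubt the primary result or the testing hierarchy. The documents do not support that: the primary analysis uses non-responder imputation, power exceeds 99%, and this analysis does not feed the hierarchy. The change is worth making so that the treatment-policy result estimates what it claims to.

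**What to change.** Amend SAP 4.2.2.5 as follows:

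- Keep all observed off-treatment values; do not reset them to missing.
- Values missing while on treatment: within-arm imputation as now.
- Values missing after discontinuation, BKZ and placebo: the placebo-based sequential model of 4.2.2.3 for each ACR component. Alternatively, impute from same-arm subjects observed off treatment, provided a minimum number stated in advance is available.
- ADA: 4.2.2.3 covers only BKZ and placebo, while 8.1.4 asks for adjusted rates in every treatment group. As ADA is descriptive only, keep within-arm imputation and say so.
- State that the Step 3 rule setting visits after an intercurrent event to non-response does not apply to this analysis.

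The cost is a few sentences and modest programming, since reference-based imputation of the ACR components is already planned in 8.1.4.4(b). The downside is a slightly smaller BKZ effect in this supportive analysis.

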4.2.3 Handling of missing data for AEs

For analyses of AEs, a complete date must be established to correctly identify the AE as occurring during treatment or not. For purposes of imputing missing components of partially reported start and stop dates for AEs, the algorithms listed below will be followed. In the event of ambiguity or incomplete data which makes it impossible to determine whether the AE was treatment-emergent, the AE will be considered treatment-emergent.

Although the algorithms for treatment-emergence depend on the start date, imputation rules are provided for stop date as well, as these may be needed for certain statistical analyses, such as an analyses of AE prevalence or AE duration.

Start and stop dates of AEs will be displayed as reported in the subject data listings (ie, no imputed values will be displayed in data listings).

Imputation of partial AE start dates

- If only the month and year are specified:
 - if the month and year of first dose of IMP is not the same as the month and year of the start date, then use the 1st of the month
 - if the month and year of first dose of IMP is the same as the month and year of the start date, then use the date of first dose of IMP
 - if the subject did switch treatment during that month and year from placebo to BKZ at Week 16, then use the date of treatment switch.
- If only the year is specified:
 - if the year of first dose is not the same as the year of the start date, and if the subjects did not switch from placebo to BKZ at Week 16 during that year then use January 1 of the year of the start date
 - if the year of first dose is not the same as the year of the start date, and if the subjects did switch from placebo to BKZ at Week 16 during that year then use the date of treatment switch
 - if the year of first dose is the same as the year of the start date and the same as the year the subject did switch from placebo to BKZ at Week 16, then use the date of first dose.
- If the date is completely unknown:
 - use the date of first dose of IMP if the stop date is unknown or not prior to the onset date

Imputation of Partial Stop Dates

- If only the month and year are specified, then use the last day of the month
- If only the year is specified, then use December 31st of that year
- If the stop date is completely unknown, do not impute the stop date.

If the imputed stop date is prior to the imputed start date:

- For missing start day and start month:
 - If the year of start date is the same as the year of first dose and the imputed stop date is on or after the date of first dose, then set the start date to the date of first dose
 - Otherwise set to the 1st January of the year of the start date.
- For missing start day only
 - If the month and year of the start date is the same as the month and year of first dose and the imputed stop date is on or after the date of first dose, then set the start date to the date of first dose
 - If the month and year of the start date is the same as the month and year of first dose and the imputed stop date is before the date of first dose, then set the start date to the 1st of that month.

In the event of ambiguity or incomplete data which makes it impossible to determine whether an AE is treatment-emergent, the AE will be considered as treatment emergent.

Other imputations

In addition, the following imputations will be applied when presenting AE in summary tables:

- if the intensity of an AE is unknown, it will be considered as severe
- If the relationship to study drug is missing, it will be considered as related

No imputation rule will be applied for missing seriousness.

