3.6.5 Active Medication Set

The Active Medication Set (AMS) will consist of all subjects who have received at least 1 dose of active IMP (BKZ or ADA). The AMS will cover the analysis of data collected during the Active Medication Periods (AMP), ie:

- The ATP for subjects randomized to placebo,
- The DBP and the ATP for subjects randomized to BKZ or ADA.

The AMS will be used for summaries of safety during the AMP.

The anti-BKZ antibody will also be analyzed on the AMS for subjects receiving BKZ.

In this analysis set, the order of the treatment groups presented in tables from left to right will be:

- BKZ Total (all BKZ treated subjects)
- ADA 40mg Q2W.

For the analysis of the compliance, study medication and time at risk, the order of the treatment groups to be presented in tables from left to right will be:

- Placebo / BKZ 160mg Q4W
- BKZ 160mg Q4W
- BKZ 160mg Q4W Total (all BKZ treated subjects)
- ADA 40mg Q2W.

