10.2 Adverse events

An AE is any untoward medical occurrence in a patient or clinical investigation subject administered a pharmaceutical product that does not necessarily have a causal relationship with this treatment. An AE can therefore be any unfavorable and unintended sign (including an abnormal laboratory finding), symptom, or disease temporally associated with the use of a medicinal (investigational) product, whether related or not to the IMP.

AEs (including SAEs) are characterized as either non-treatment or treatment-emergent according to the following criteria:

- Non treatment-emergent are the events with onset date and time prior to the very first administration of study medication (BKZ or placebo) or after a 140-day period after the final drug administration.
- Treatment-emergent AEs (TEAE) are those with onset date at or after the very first administration of study medication. The events that emerge within 140 days after the final drug administration, will also be considered as treatment-emergent (eg, in the case of premature discontinuation or during the SFU Period).

If an AE occurs on the same day as the treatment switch (Week 16, to BKZ for subjects randomized to Placebo) then the AE will be allocated to the Double-Blind Treatment. An exception from this general rule is made for the following types of AEs that will be allocated to the BKZ:

- Events that fulfill the anaphylaxis criteria for acute events (refer to Appendix 1)
- Events that fulfill the hypersensitivity reaction criteria (refer to Appendix 1)
- Events with a high-level term (HLT) of “Administration site reactions NEC”
- Events with an HLT of “Injection site reactions”

The incidence of TEAEs will be summarized descriptively by treatment group, MedDRA primary system organ class (SOC), HLT, and preferred term (PT).

AEs will be presented as “number of subjects (percentage of subjects) [number of events]”. In this style of output, “[number of events]” will include all cases of an AE including repeat occurrences in individual subjects, while “number of subjects” will count each subject only once.

Adverse event summaries by SOC, HLT and PT will be ordered alphabetically for SOC and HLT within SOC and in terms of decreasing frequency for PT within HLT in the BKZ treatment group and then similarly by decreasing frequency in the placebo group.

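### AEs of placebo switchers whose start date is imputed to the switch date are counted under placebo for all but four event types, and two month-only imputation rules conflict

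*SAP*

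**What the plan says.** **SAP 4.2.3, month and year known.** The switch-date bullet covers a subject who "did switch treatment during that month and year from placebo to BKZ at Week 16, then use the date of treatment switch". An earlier bullet in the same list applies "if the month and year of first dose of IMP is not the same as the month and year of the start date"; its result is the first day of the month. It has no carve-out for switchers, and no order of precedence is stated.

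**SAP 4.2.3, only the year known.** Where first dose and start date fall in different years, "if the subjects did switch from placebo to BKZ at Week 16 during that year then use the date of treatment switch". Where first dose and switch share the year, the date of first dose is used. A completely unknown start date also goes to first dose.

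**SAP 4.2.3, stated purpose.** The section says that "a complete date must be established to correctly identify the AE as occurring during treatment or not".

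**SAP 10.2.** The same-day rule opens with the condition "If an AE occurs on the same day as the treatment switch" and ends with the allocation "then the AE will be allocated to the Double-Blind Treatment". Four event types go to BKZ instead: events meeting the anaphylaxis criteria, events meeting the hypersensitivity criteria, and two high-level terms for administration-site and injection-site reactions. TEAEs are placed in periods by their date of emergence.

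**SAP 3.6.5.** The Active Medication Period (AMP) is defined by randomized arm: "The ATP for subjects randomized to placebo", against both periods for the other two arms.

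**SAP 4.2.4.** The parallel first-of-the-month rule for medications does exclude subjects who switched in that month.

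**The concern.** Each rule is reasonable alone. A same-day rule for observed dates is understandable, because the first ATP dose is given after the Week 16 assessments (SAP 2.3.2.3). That reasoning does not carry over to a date that was assigned because the true day is unknown.

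Once the two rules are chained, an AE that may have started on BKZ is moved to the placebo column of the double-blind tables and does not enter the BKZ columns of the ATP or AMP tables. Among switchers the movement is in one direction only. It also touches the controlled comparison. SAP 10.2.4.9 reports double-blind risk differences (BKZ minus placebo) for topics such as serious infection, neutropenia, IBD and hepatic events, and an extra affected placebo subject lowers that difference.

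Separately, two month-only rules give different dates for the same record, so two programmers could produce different tables.

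**Working it through.** The SAP states no figure on this point, so there is none to reproduce. The check applies the rules in sequence.

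**1. Which month-only bullets can apply in the switch month?** The double-blind period is 16 weeks = 112 days. Taking 730 consecutive first-dose dates with the switch 112 days later, first dose and switch share a calendar month in 0 of 730 cases. The first-dose bullet therefore never applies in the switch month. The first-of-the-month bullet and the switch-date bullet both always apply.

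**2. Where does the AE end up?**

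| Bullet used in 4.2.3 | Imputed date | Non-exempt AE | Exempt event type |
|---|---|---|---|
| Switch date | Switch day | Placebo, by the same-day rule | BKZ, by the exception |
| First of month | On or before the switch day | Placebo | Placebo, unless the switch is itself on the 1st |

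Non-exempt AEs go to placebo in 100% of cases under either bullet. For exempt types the bullet chosen decides the column.

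**3. Does the AE reach a BKZ table?** The AMP of a placebo-randomized subject is the ATP only (3.6.5). An AE placed in the double-blind period is therefore in neither the ATP tables nor the BKZ Total. The default to treatment-emergent in 4.2.3 does not help, because the AE is already treatment-emergent on placebo.

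**4. What share would have begun after the switch?** Assume onset is uniform over the switch month. For a switch on day *d* of a month with *L* days, the share after the switch day is (*L* − *d*)/*L*. Averaged over *d*, this is (*L* − 1)/(2*L*):

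- *L* = 30: 29/60 = 48.3%
- *L* = 31: 30/62 = 48.4%

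Over the 730 dates (22,248 possible onset days) the result is 48.4%. The range runs from 0% (switch on the last day of the month) to 30/31 = 96.8% (switch on the 1st of a 31-day month). The share of non-exempt AEs allocated to BKZ is 0%.

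**5. How wide is the year-only case?** It needs first dose and switch in different calendar years: 224 of 730 = 30.7% of first-dose dates. For the other 506, 4.2.3 itself sends a year-only AE to first dose.

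**6. What does the switch-date bullet achieve?** Without it, the AE would be dated the 1st of the month and would already be treatment-emergent on placebo. The bullet can change treatment allocation only by moving the event to BKZ. Section 10.2 cancels that for everything except the four exempt types.

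**The case against.** **The same-day rule may cover observed dates only.** Section 10.2 does not mention imputed dates, whereas 10.2.6 does so expressly for the COVID-19 periods. Section 2.3.2.3 starts the ATP on the Week 16 dosing day, which points away from a double-blind allocation. This stands to the extent that applying the rule to imputed dates is an inference. It is the natural one: 4.2.3 requires a complete date to place an AE, and nothing separates imputed from observed dates.

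**The SAP may not intend doubtful AEs to go to BKZ.** A reader might infer that this was plainly the aim. The documents do not say so. The tie-break is to treatment-emergent, not to BKZ, and other ambiguous dates of switchers go openly to first dose. The argument in step 6 shows only that the switch-date bullet has almost no effect on allocation as things stand.

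**The events are not lost.** A reader might infer that all ambiguous AEs disappear. They do not. The four exempt types can reach BKZ, and the others remain in the double-blind tables and in the listings, where dates are shown as reported.

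**The effect is small.** Probably so. Site visits every two weeks should keep partial dates rare. The 280 planned placebo subjects are an upper limit on switchers, since some may withdraw before Week 16. No SAE or safety-topic event is known to be affected.

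**The month-rule overlap is only drafting.** The switch-date bullet can be read as the specific case that overrides the general one. That is likely what was meant: the year-only bullet in 4.2.3 and the month bullet in 4.2.4 both carry the exclusion. It still has to be written, because the exempt types change column.

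**Conclusion.** The point holds in limited form. For placebo subjects who switch, non-exempt AEs whose start date is imputed to the switch date are counted under placebo and are missing from the BKZ columns of the ATP and AMP tables, although about 48% of the month-only ones (range 0% to 97%) would have begun after the switch. This rests on three assumptions: the same-day rule covers imputed dates, onset is uniform over the month, and the switch is at day 112. The contradiction between the two month-only bullets does not depend on the first two of these.

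The number of affected AEs cannot be derived, because the SAP gives no rate of partial dates; it is probably small. The case for changing it is that the misallocation runs one way, that it can enter tables of rare safety topics where single events count, and that the correction is short.

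**What to change.** - **Section 10.2:** limit the same-day rule to AEs with a fully reported start date. State that an AE whose start date was imputed to the switch date is allocated to BKZ, in the ATP and the AMP.
- **Section 4.2.3:** add to the first-of-the-month bullet the condition that the subject did not switch from placebo to BKZ in that month and year, as 4.2.4 already does.

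**Cost.** Two or three sentences and a small programming change. The share of these AEs charged to placebo falls from 100% to 0%, but the change alters the direction of the error rather than removing it. Under uniform onset about 52% (100% − 48%) began on or before the switch day and would now be counted under BKZ. That is the conservative direction for BKZ safety. The Week 24 AE tables are rerun at Week 52 (SAP 10.2.5), so a few AEs may move between columns and a short reconciliation note may be needed.
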